10.6.3 Laboratory Test Results

Shifts in grades of safety laboratory values between the baseline and the worst on-study value will be tabulated overall and by dose level group(if applicable). See Protocol Table 3 for list of laboratory analytes.

A listing will be provided for subjects in the qPCR Analysis Set by assessed time point of qPCR analysis results (positive, and numeric value if quantifiable) for talimogene laherparepvec DNA in swab samples taken from cold sore, vesicles, and other lesions suspected to be herpetic in origin.

10.6.4 Vital Signs

Descriptive statistics will be presented for systolic/diastolic blood pressure, heart rate, respiratory rate, temperature and temperature for baseline, each post-baseline visit, change from baseline, and percent change from baseline.

10.6.5 ECOG Performance Scores

Shifts in scores for ECOG performance status scores between baseline and safety follow-up will be tabulated.

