^a Up to approximately 18 subjects will be enrolled in the study. Subjects may be included in the evaluation for both safety and efficacy. The DLT evaluation period is 35 days from the initial administration of talimogene laherparepvec. Initially, 6 DLT-evaluable subjects will be enrolled and treated at Dose 1. Upon demonstration of safety based on DLT rules, an additional 12 subjects will be enrolled and treated at Dose 1 to obtain additional safety data. However, if Dose 1 is declared unsafe based on DLT rules, then an additional 6 DLT-evaluable subjects will be enrolled at Dose -1.

^b Treatment will continue until subject experiences a DLT (during the DLT evaluation period), subject achieved a CR, no injectable lesions, clinically relevant (resulting in clinical deterioration or requiring change of therapy) disease progression beyond 24-weeks of treatment, per modified WHO response criteria, safety concern, a maximum treatment duration of 48 months, or the drug is commercially available in Japan, whichever occurs first.

Product: Talimogene Laherparepvec

Protocol Number: 20140270

Date: 01 September 2020

Page 9 of 98

Study Glossary

Abbreviation or Term	Definition/Explanation
ALT	alanine aminotransferase
AST	aspartate aminotransferase
BOR	best overall response
BRAF ^{V600E/K}	serine/threonine protein kinase B-Raf V600E/K
CI	confidence interval
CNS	central nervous system
CR	complete response
CRF	case report form
CT	computed tomography
CTCAE	Common Terminology Criteria for Adverse Events
DILI	drug-induced liver injury
DLRT	Dose Level Review Team
DLT	dose limiting toxicity
DOR	duration of response
DR	durable response
DRR	durable response rate
ECG	electrocardiogram
ECOG	Eastern Cooperative Oncology Group
EDC	electronic data capture
End of Study for Individual Subject	The last day that protocol-specified procedures are conducted for an individual subject (ie, the date the subject withdraws full consent from the study, completes the safety follow-up visit or long-term follow-up [whichever is later] or death).
End of Study (primary completion)	The date when the last subject is assessed or receives an intervention for the final collection of data for the primary endpoint(s), for the purpose of conducting the primary efficacy analysis, whether the study concluded as planned in the protocol or was terminated early. This will be the date when the last subject has been assessed for a durable response outcome.

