^g If subject discontinues talimogene laherparepvec for a reason other than disease progression or death, tumor measurements are to be performed at the safety follow-up visit (if not performed within previous 4 weeks [+ 1 week]) and every 12 weeks (+ 1 week) during the long-term follow-up period until PDr beyond 6 months of treatment (per modified WHO response criteria as described in [Appendix D](#)) or until the start of a new anticancer therapy. **Long-term follow-up is not applicable for subjects treated beyond 24 months after the last subject is enrolled.**

^h The tumor assessment, physical exams, and ECOG performance status will be completed after 12 (\pm 1) weeks on treatment (ie, day 1 of week 11), and then every 12 (\pm 1) weeks (eg, weeks 23, 35, 47 etc.), or more frequently if clinically indicated, until PDr beyond 6 months of treatment (per modified WHO response criteria [see [Appendix D](#)]) or until the start of a new anticancer therapy.

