7.2.4 Follow-up

7.2.4.1 Safety Follow-up

Upon permanent discontinuation from the study treatment for any reason, a safety follow-up visit will be performed 30 (+7) days after the last dose of talimogene laherparepvec. The safety follow-up visit is not required for those subjects who are enrolled, but did not receive any dose of investigational product.

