10.4.4 Safety Endpoints

Subject incidence of treatment emergent adverse events will be tabulated by system organ class and preferred term. Treatment-emergent adverse events are defined as adverse events with an onset from the first dose of study therapy up to 30 days after the last dose of study therapy. Tables of fatal adverse events, serious adverse events, all adverse events, and adverse events leading to withdrawal from investigational product, will be provided.

Subject incidence of disease- related events and fatal disease- related events will be tabulated by system organ class and preferred term.

Medical Dictionary for Regulatory Activities will be used to code adverse events to a system organ class and a preferred term within the system organ class. CTCAE version 4.0 will be used to grade severity of adverse events.

Summary statistics over time will be provided for selected key safety laboratory endpoints. Shifts in grades of these safety laboratory endpoints between the baseline and the worst on-study value will be tabulated by dose level group.

The ECG measurements from this clinical study will be performed as per standard of care for routine safety monitoring, rather than for purposes of assessment of potential QTc effect. Since these evaluations may not necessarily be performed under the rigorous conditions expected to lead to meaningful evaluation of QTc data. Summaries and statistical analyses of ECG measurements are not planned, and these data would not be expected to be useful for meta-analysis with data from other trials.

Subject incidence of suspected herpetic lesions along with data from qPCR analysis performed to detect talimogene laherparepvec DNA will be reported.

Potential or known unintended exposure to talimogene laherparepvec, related suspected signs or symptoms, and detection of talimogene laherparepvec in a subject's household member, caregiver, or healthcare provider will be reported.

Summary statistics will also be provided for concomitant medications, dose delay, study drug discontinuation, overall exposure, and ECOG performance status.

Summary statistics will be provided for vital signs and other physical measurements. Details of the analysis will be provided in statistical analysis plan.

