8.2 Primary Analysis

The primary analysis for safety will occur 3 months after the last subject is enrolled. The primary analysis for efficacy will occur when a durable response outcome has been assessed for all subjects included in the primary efficacy analysis. Safety will be re-analyzed at the primary efficacy analysis.

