8.3 Final Analysis

The final analysis will occur 24 months after the last subject is enrolled.

If there are subjects who receive therapy beyond 24 months, a post final analysis of these subjects will occur after the last subject completes safety follow-up.

Adverse events and tumor assessments evaluated after final analysis will be listed for these subjects.

9. Data Screening and Acceptance

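### The SAP's only post-baseline ECOG output is a shift to the post-treatment safety follow-up visit, so subjects without that visit contribute no shift and the scheduled on-treatment values go unused, mainly at the primary safety analysis

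*SAP*

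**What the plan says.** SAP 10.6.5 consists of one sentence: "Shifts in scores for ECOG performance status scores between baseline and safety follow-up will be tabulated". The only other ECOG output in the SAP is the baseline summary in SAP 10.4.

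Protocol 7.2.4.1 places the visit after treatment has permanently stopped: "a safety follow-up visit will be performed 30 (+7) days after the last dose of talimogene laherparepvec". Treatment may continue up to "a maximum treatment duration of 48 months, or the drug is commercially available in Japan, whichever occurs first" (Protocol, Study Design and Treatment Schema, footnote b). Protocol 6.2.1.1 asks for at least 24 weeks of treatment, even through progression, unless other melanoma therapy is needed.

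ECOG is collected well before that visit. Protocol Table 2 schedules it at screening and day 1, and footnote h adds the on-treatment values: "The tumor assessment, physical exams, and ECOG performance status will be completed after 12" weeks (taken at week 11), then every 12 weeks. Footnote e extends collection into long-term follow-up for subjects who stop for reasons other than progression or death.

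On timing, SAP 8.2 states "The primary analysis for safety will occur 3 months after the last subject is enrolled", with safety re-analyzed at the primary efficacy analysis. SAP 8.3 states "The final analysis will occur 24 months after the last subject is enrolled". For subjects treated beyond that point, SAP 8.3 adds "Adverse events and tumor assessments evaluated after final analysis will be listed for these subjects". Protocol 10.3.4 is broader and promises a summary of safety and efficacy data collected after the final analysis. Protocol 10.4.4 promises ECOG summaries without tying them to a visit: "Summary statistics will also be provided for concomitant medications, dose delay, study drug discontinuation, overall exposure, and ECOG performance status".

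**The concern.** A table that needs a post-treatment visit depends on who has stopped treatment and lived to attend. At any data cut it has no shift for subjects still on drug, nor for those who die, withdraw consent in full or are lost within about a month of the last dose. Both routes are related to outcome. The table also describes one moment after treatment, not performance status on treatment.

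The on-treatment values matter to a reader because a decline in performance status is one of the criteria that make progression clinically relevant (Protocol Appendix D, Tables 5 and 6). That classification governs whether treatment continues after 24 weeks. In an open-label, investigator-assessed study, an on-treatment ECOG summary is a simple way to see those decisions in context.

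At stake is the completeness of a descriptive safety table in about 18 subjects, not an inferential result.

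**Working it through.** The plan gives no figure for this table, so there is nothing to reproduce. The check is of the text and the visit timeline.

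**1. Comparison with neighboring SAP sections**

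| Measure | SAP section | Post-baseline time used |
|---|---|---|
| Laboratory grades | 10.6.3 | worst on-study value |
| Vital signs | 10.6.4 | every post-baseline visit |
| ECOG | 10.6.5 | safety follow-up only |
| Weight | 10.6.6 | every assessed time point |

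ECOG alone rests on one post-treatment visit.

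**2. Scheduled on-treatment ECOG values left out, per subject still on drug**

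With visits at weeks 11, 23, 35 and so on, and one month = 365.25/7/12 = 4.35 weeks:
- 3 months = 13.0 weeks: 1 value (week 11).
- 24 months = 104.4 weeks: 8 values (weeks 11 to 95).
- 48 months = 208.7 weeks: 17 values (weeks 11 to 203).

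**3. Who can have the visit at the primary safety analysis**

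The visit falls at least 30/7 = 4.3 weeks after the last dose. A subject treated for the intended minimum has it no earlier than 24 + 4.3 = 28.3 weeks after starting. The cut comes 13.0 weeks after the last enrollment. Anyone enrolled in the last 28.3 − 13.0 = 15.2 weeks of accrual (unrounded inputs) and treated for at least 24 weeks therefore cannot contribute. The length of accrual is not stated, so this cannot be turned into a count.

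**4. Illustrative size (assumptions, not document figures)**

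Assume exponential time on treatment with median M and no deaths. For a subject followed w weeks to the cut, P(no safety follow-up visit yet) = 0.5^((w − 4.29)/M). Protocol 2.2 gives a phase 3 median of 23 weeks; half and double that value show the range.

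| Time from enrollment to cut | w − 4.29 (weeks) | M = 11.5 | M = 23 | M = 46 |
|---|---|---|---|---|
| 3 months | 8.76 | 59% | 77% | 88% |
| 6 months | 21.80 | 27% | 52% | 72% |
| 12 months | 47.89 | 6% | 24% | 49% |
| 24 months | 100.07 | 0.2% | 5% | 22% |

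At the final analysis, 24 months is the shortest possible follow-up. The M = 23 figure therefore gives at most 18 × 0.049 = 0.9 subjects, reached only if all 18 were enrolled last. Deaths and losses before the visit come on top and cannot be estimated from the documents.

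**5. Weight of one subject**

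Each subject without a shift is 1/18 = 5.6% of the safety set.

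**6. After the final analysis**

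The last-enrolled subject could be on drug up to 48 − 24 = 24 months beyond that cut. SAP 8.3 does not name ECOG among the post-final outputs; Protocol 10.3.4 would cover it as safety data.

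**The case against.** The strongest reply is that this is a presentation choice. ECOG is not a primary, secondary or listed safety endpoint, and the table feeds no test, DLT rule or named decision. Protocol 10.4.4 fixes no time point, so a shift to safety follow-up satisfies it. That stands: there is no contradiction with Protocol 10.4.4, and the point is minor.

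Much of the gap at the first cut is also temporary, since safety is re-analyzed at the primary efficacy analysis and again at the final analysis. That stands too, and is why the point is mainly about the primary safety analysis. It does not help subjects who never reach the visit, and it brings no on-treatment value into any table.

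A reader might infer more than the documents support:
- **That the best-doing subjects are systematically lost.** Treatment stops at complete response or when no injectable lesions remain (Protocol 6.2.1.1 and 6.2.2), and those subjects do get the visit. Only subjects still on drug are affected.
- **That stopping treatment early removes a subject.** Discontinuation for any reason triggers the visit (Protocol 7.2.4.1). Only death, full withdrawal of consent, loss to follow-up or a missed visit removes the value.
- **That missing subjects vanish from view.** The SAP gives no display rule, so a missing row is possible, and SAP 10.2 reports reasons for not completing the 30-day visit. Deaths also appear in OS and the fatal-event outputs. They would still contribute no ECOG shift.
- **That late ECOG values can never be reported.** Protocol 10.3.4 promises a summary of post-final safety data. The fair statement is that SAP 8.3 does not name ECOG.
- **That a sixth to a third of subjects (3 to 6 of 18) will be missing.** No document gives such a count.

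**Conclusion.** The point holds as a minor gap in descriptive reporting. The only post-baseline ECOG output named in the SAP requires a visit that exists only after permanent discontinuation. Scheduled on-treatment values are unused, and no rule covers subjects who die or are lost before the visit (Protocol Appendix E has a grade for death, but nothing assigns it here).

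The gap is largest at the primary safety analysis. Under the 23-week exponential assumption, about 77% of subjects enrolled 3 months earlier would lack the visit, with a range of 59% to 88% for half to double that median. At the final analysis the on-treatment part is probably small: about 5% for a last-enrolled subject, rising to 22% if the median were twice as long. These figures borrow a median from a study with different stopping rules and ignore deaths. The actual number affected is not in the documents.

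It would be too strong to call the trial's safety conclusions biased. The table is descriptive with no stated estimand, and the DRR test and the DLT rule do not depend on it.

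**What to change.** In SAP 10.6.5, add a shift from baseline to the worst post-baseline ECOG for the whole safety analysis set, in line with the worst on-study convention of SAP 10.6.3. Give it an explicit missing/death category, and keep the safety follow-up shift as a second column. State the window for the worst value, including whether long-term follow-up assessments count, since only some subjects have them.

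In SAP 8.3, add ECOG to the outputs for subjects treated beyond the final analysis, so that the section agrees with Protocol 10.3.4.

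The cost is SAP wording, one extra table column and one listing, all from data already collected. No visits are added, and the sample size, alpha and power do not change.

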10.6.6 Physical Measurements

Height and weight will be summarized at each assessed time point. The change in weight and percent change in weight from baseline to each assessed time point will also be summarized.

10.6.7 Electrocardiogram (ECG)

The ECG measurements from this clinical study were performed as per standard of care for routine safety monitoring, rather than for purposes of assessment of potential QTc effect. Because these evaluations may not necessarily be performed under the rigorous conditions expected to lead to meaningful evaluation of QTc data; neither summaries nor statistical analyses will be provided, and these data would not be expected to be useful for meta-analysis with data from other trials.

10.6.8 Antibody Formation

Baseline HSV-1 serostatus will be summarized.

The incidence of HSV-1 seroconversion will be summarized for subjects that are baseline seronegative.

10.6.9 Exposure to Investigational Product

Descriptive statistics will be produced to describe the exposure to investigational product. Summary statistics for exposure to talimogene laherparepvec, including total doses administered, total volume administered, duration from the first to the last administration of talimogene laherparepvec, and the average volume received by subject per visit will be provided and will be separated by the first (concentration of 10^6 PFU/mL) and subsequent doses (concentration of 10^8 PFU/mL or 10^6 PFU/mL). Subject incidence rate and reasons for IP delay, dose change and withdrawal will be tabulated.

10.6.10 Exposure to Concomitant Medication

The number and proportion of subjects receiving therapies of interest will be summarized by preferred term or category overall and for each dose level as coded by the World Health Organization Drug (WHO DRUG) dictionary.

11. Literature Citations / References

Clopper, C., *et al* (1934) "The Use of Confidence or Fiducial Limits Illustrated in the Case of the Binomial" *Biometrika*, **26**, 404-413

[figure not shown]
Kalbfleisch, J.D. and Prentice, R.L. (1980) *The Statistical Analysis of Failure Time Data*, New York: John Wiley & Sons

[figure not shown]
Brookmeyer R. and Crowley J. (1982) "A Confidence Interval for the Median Survival Time" *Biometrics*; **38**, 29-41

Andtbacka R., *et al* (2015) "Talimogene Laherparepvec Improves Durable Response Rate in Patients With Advanced Melanoma." *Journal of Clinical Oncology*; 33(25), 2780-2788

12. Appendices

Appendix A. Conventions for Clinical Data That Require Imputation for Partial or Missing Date

Appendix B. Cutoff Values for qPCR Assay

The current assay cutoff values are as follows:

For qPCR, the cutoff (LLOQ) is 0.6 (1.76) copies/ μ g for blood, 5.8 (24) copies/ μ g for urine, and 7.5 (18) copies/ μ g for swabs.

For the most recent cutoff and LLOQ values and other details regarding their determination, refer to the following validation report:

Validation Report to Establish the Performance Characteristics of the Talimogene Laherparepvec (T-VEC) Quantitative and Qualitative Real Time PCR (qPCR) assay in Whole Blood, Swabs and Urine qPCR (see table on page 6 in the validation report for qPCR LLOD and LLOQ values)

Table B1. Definition of qPCR Results

| | Viracor Result to be reported | Result Unit | Definition of Results | Amgen T-VEC qPCR result Definition | |
|---------------------------|-------------------------------|---------------------|----------------------------|------------------------------------|------------------|
| Blood/ Urine/ Swabs | Number | Copies/ μ g DNA | \geq LLOQ | Positive | Quantifiable |
| | Detected BQL | NA | \geq cutoff and $<$ LLOQ | | Non-quantifiable |
| | Not detected | NA | $<$ cutoff | Negative | |

Table B2. Cutoff Values for qPCR Results Definition*

| | LLOQ (Copies/ μ g DNA) | cutoff (Copies/ μ g DNA) |
|-------|----------------------------|------------------------------|
| Blood | 1.76 | 0.6 |
| Urine | 24 | 5.8 |
| Swabs | 18 | 7.5 |

* The analytical method has no upper limit of quantitation.
